10.3 Screening and Study Visits

The study site is responsible for maintaining an enrollment/screening log that includes all subjects enrolled. The log also will serve to document the reason for screening failure. All screening data will be collected and reported in CRFs, regardless of screening outcome. If a subject does not satisfy ALL inclusion criteria at screening, the subject may be re-screened at a later time at the discretion of the investigator. The investigators will determine all monitoring schedules, including the frequency of clinic visits and laboratory testing. A screening visit during which the investigator determines whether the enrolled subject (ie, one whose legally authorized representative(s) has signed an ICF) meets all inclusion criteria and none of the exclusion criteria is required. All other study visits, including the last visit, should coincide with the routinely and emergently scheduled clinic and hospital visits that the subject has in the 6-month period following enrollment.

10.3.1 Screening Visit

The following data will be collected at the **screening visit**:

- Date of birth
- Gender
- Race

- Ethnicity
- Height (cm)
- Weight (kg)
- Medical history
 - ➤ History of local and general infusion-related reactions
 - ➤ History of hypersensitivity reactions
 - ➤ History of FVIII inhibitor, if any
 - Date of inhibitor detection
 - o Date of inhibitor disappearance
 - o Titer at time of inhibitor detection
 - o Maximum historical titer
 - o Total FVIII ED at time of inhibitor detection
 - o FVIII product used at time of inhibitor detection
 - o FVIII regimen used at time of inhibitor detection
 - History of ITI therapy, if any, including FVIII product and regimen used
 - Most recent FVIII inhibitor titer
- Concomitant medications, including vaccinations
- Vaccination status for hepatitis A virus (HAV) and hepatitis B virus (HBV), if available
- Serology for hepatitis C virus (HCV) and human immunodeficiency virus type 1 & 2 (HIV-1/2), if available
- Baseline FVIII level
- FVIII mutation genotype, if available
- Family history of inhibitors
- Local laboratory cut off value for positive inhibitor titer
- Current treatment regimen (eg, prophylaxis or on-demand) with ADVATE reconstituted in 2 mL SWFI
 - Weight adjusted dose and dosing interval (frequency of infusions)
 - > Regimen start date
 - > Total FVIII ED at study entry
 - o For subjects with ≤50 EDs at study entry, exact number of total EDs must be recorded

- For subjects with >50 EDs, exact number of total ED is preferred, however, if this data is not available, one of the following ranges should be selected: 51 100, 101 150, > 150 ED
- > FVIII inhibitor titer at study entry
- > FVIII incremental recovery (IR; IU/dL per IU/kg) at study entry, if available
- Prior to study entry (maximal retrospective time period of 2 years)
 - > Treatment regimen (eg, prophylaxis, on-demand, or ITI)
 - Weight adjusted dose and dosing interval (frequency of infusions)
 - o Regimen start and end date
 - Name and/or type of products prior to ADVATE, if applicable
 - o Plasma-derived FVIII with VWF, intermediate purity
 - o Plasma-derived FVIII without VWF, high purity
 - o Recombinant FVIII: generation category; full-length vs. B-domain deleted molecule

10.3.2 Interval and Termination Visits

The following data, if available, will be collected at **interval and termination visits**:

- Height (cm)
- Weight (kg)
- Treatment regimen (eg, prophylaxis or on-demand) with ADVATE reconstituted in 2 mL SWFI
 - Weight adjusted dose and dosing interval (frequency of infusions)
 - Regimen change date
- All serious and non-serious AEs, regardless of causal relationship to ADVATE reconstituted in 2 mL SWFI
- All local and general, hypersensitivity and infusion-related reactions (see Appendix A for example only)
- FVIII inhibitor titer
- Serology for HCV and HIV-1/2, if available
- FVIII IR (IU/dL per IU/kg)
- Total ED from ADVATE reconstituted in 2 mL SWFI during study
- Total ED from all FVIII therapies

- Concomitant medications, including vaccinations
- Bleeding episodes, including anatomical location, etiology, and severity
- Subjective hemostatic effectiveness rating of excellent, good, fair, or none for each bleeding episode
- Number of ADVATE reconstituted in 2 mL SWFI infusions used to treat each bleeding episode
- Total units of ADVATE reconstituted in 2 mL SWFI administered to treat each bleeding episode
- Overall effectiveness assessment for prophylaxis for subjects who are on a prophylactic regimen for full duration of study (6 months), at termination visit
- Number of days subject missed from school/daycare due to each bleeding episode
- Number of days subject's caregiver missed from work/school/normal daily activities due to each bleeding episode

Details on the procedures to be performed at each study visit, including screening, can be found in Supplement 21.1 Schedule of Study Procedures and Assessments.

10.3.3 Surgical or Dental Procedures

For subjects who undergo surgical or dental procedures during the study, the following data will also be collected, as available:

- Type of procedure
- Date and time of procedure
- Mode of ADVATE administration
- Total weight-adjusted dose of ADVATE infused in the preoperative, intraoperative, and postoperative periods
- Total number of days of FVIII replacement therapy
- Global assessment of intraoperative and postoperative hemostatic effectiveness as determined by the investigator (excellent, good, fair, or none)

10.4 Medications and Non-Drug Therapies

The use of another FVIII concentrate, other than ADVATE reconstituted in 2 mL SWFI, is **not** permitted during the course of the study. A subject who uses a FVIII concentrate other than ADVATE will be considered a protocol violation. The use of ADVATE reconstituted in 5 mL SWFI will be considered a protocol deviation.

Subjects may receive ADVATE reconstituted in 5 mL SWFI if a higher potency is needed for adequate hemostatic coverage during emergent surgical procedures, but this will be considered a protocol deviation. As the administration of ADVATE reconstituted in 5 mL SWFI for surgical prophylaxis would constitute a discrete episode, these subjects may be able to continue participation in the study. Please liaise with the medical monitor for the study when any such deviation is foreseen.

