8. STUDY DESIGN

8.1 Overall Study Design

This study is a prospective, non-interventional PASS study that assesses the safety and effectiveness of ADVATE reconstituted in 2 mL SWFI during routine clinical practice. Subjects with severe or moderately severe hemophilia A (FVIII ≤2%) and documented prior exposure to FVIII concentrates, aged ≤12 years, who are prescribed ADVATE and will only receive ADVATE reconstituted in 2 mL SWFI, will be asked to participate. The study will prospectively capture ADVATE related data for 6 months from the date of enrollment. Subjects should receive all FVIII therapy with ADVATE reconstituted in 2 mL SWFI during the study observation period. The investigators shall determine all treatment regimens according to product labeling information and standard practice. For all bleeding episodes requiring treatment, the subject should be treated until adequate hemostasis is achieved. The investigators will also determine all monitoring schedules, including the frequency of clinic visits and laboratory testing. A screening visit during which the investigator determines whether the enrolled subject (ie, one whose legally authorized representative(s) has signed an informed consent form [ICF]) meets all inclusion criteria and none of the exclusion criteria is required. All other study visits, including the last visit, should coincide with the routinely and emergently scheduled

clinic and hospital visits that the subject has in the 6-month period following enrollment. Caregivers will be asked to complete a short survey at the beginning and end of the 6-month observation period. The survey will capture data on their infusion experience and satisfaction with ADVATE reconstituted in 5 mL SWFI at the beginning of the study and with ADVATE reconstituted in 2 mL SWFI at the end of the study. The follow-up survey will also ask caregivers about their preferences between ADVATE reconstituted in 2 mL and 5mL SWFI on a variety of factors. This survey is strictly optional and will only be offered where such a survey is in concordance with non-interventional study regulations and after ethics committee (EC) approval of its use.

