9. SUBJECT SELECTION, WITHDRAWAL, AND DISCONTINUATION

9.1 Inclusion Criteria

Subjects who meet ALL of the following criteria are eligible for this study:

- Subject has severe or moderately severe hemophilia A (baseline FVIII ≤ 2%)
- Subject is ≤ 12 years of age
- Subject's legally authorized representative(s) has provided written informed consent
- Subject is prescribed ADVATE and will only receive ADVATE reconstituted in 2 mL SWFI
- Documented history of prior exposure to ADVATE (for subjects ≤ 2 years old, at least 3 EDs to ADVATE; for subjects with ≤ 50 EDs, all prior EDs must be to ADVATE; for subjects with >50 EDs, the last 20 prior EDs must be to ADVATE)
- Documented evidence of negative inhibitor test result during ≤10 EDs prior to study entry

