14.2.1 Safety Analysis Set

The safety analysis set (SAS) will consist of data for all subjects that receive at least 1 dose of ADVATE reconstituted in 2 mL SWFI.

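### Section 10.4 foresees 5 mL ADVATE in a study otherwise limited to 2 mL, and the safety outcomes do not separate events that follow it

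*Protocol*

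**What the plan says.** **What FVIII is allowed.** Protocol 9.1 makes it an entry condition that "Subject is prescribed ADVATE and will only receive ADVATE reconstituted in 2 mL SWFI". Section 8.1 says "Subjects should receive all FVIII therapy with ADVATE reconstituted in 2 mL SWFI during the study observation period". Section 10.4 opens with "The use of another FVIII concentrate, other than ADVATE reconstituted in 2 mL SWFI, is not permitted during the course of the study" and continues "The use of ADVATE reconstituted in 5 mL SWFI will be considered a protocol deviation"; a FVIII concentrate other than ADVATE is called a violation. The second paragraph of 10.4 then states "Subjects may receive ADVATE reconstituted in 5 mL SWFI if a higher potency is needed for adequate hemostatic coverage during emergent surgical procedures", repeats that this is a deviation, asks sites to contact the medical monitor when it is foreseen, and says that "these subjects may be able to continue participation in the study".

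**What is counted.** The safety analysis set (14.2.1) holds the data of "all subjects that receive at least 1 dose of ADVATE reconstituted in 2 mL SWFI". The primary outcome (8.3.1, 14.4.1) is the incidence of all local, general, hypersensitivity and infusion-related reactions regardless of causality, computed on that set. Under 11.1.9, adverse events are recorded from first exposure to study product until completion or discontinuation. Inhibitors (14.4.2) are counted in the safety set and in IAS1 and IAS2. Those two subsets are restricted by prior exposure days, baseline FVIII and inhibitor history (14.2.1.1, 14.2.1.2), not by the product received on study.

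**The concern.** The presentation is the exposure under study. Section 6.5.1 explains why: the smaller volume leaves less time to stop an infusion if hypersensitivity develops. A safety count for 2 mL should therefore let the reader see which events followed 2 mL and which followed something else.

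As written, it does not. The protocol foresees that some children will receive 5 mL and may continue. Their later events fall within the collection window, the analysis set and the outcome definition, and nothing marks them as following a different presentation. At stake is a correct label on a small number of safety events, in a study whose only product is a descriptive table of such events.

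**Working it through.** **1. The passages side by side**

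| Place | 5 mL ADVATE on study |
|---|---|
| 8.1 | All FVIII should be 2 mL |
| 9.1 | Child will receive 2 mL only |
| 10.4, first paragraph | Not permitted; if used, a deviation |
| 10.4, second paragraph | May be given in emergent surgery; a deviation; child may be able to continue |
| 9.3 | Withdrawal listed for inhibitors only |
| 10.6 | Physician decision is a discontinuation reason, with violations as the example; deviations are not mentioned |

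The reader can work out a rule with a narrow exception, but no single passage states it, and no criterion says when a child continues.

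**2. Tracing one event.** Take a child on regular 2 mL who receives 5 mL for emergent surgery and then has a reaction.

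- Safety set: yes, because at least one 2 mL dose was given.
- Collection window: yes, because it does not pause for 5 mL use.
- Adverse event definition (11.1): this refers to temporal association with 2 mL. A child infused regularly with 2 mL can meet it around a 5 mL dose, and 10.3.2 collects all events regardless of causal relationship.
- Reaction definition (11.1.5): an event associated with infusion, with no presentation named.
- Causality filter: none for the primary outcome.

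The event is counted in the primary outcome. An inhibitor follows the same path into the all-subjects count and, if the child qualifies, into IAS1 and IAS2.

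**3. Can the data separate it?** Section 10.3.2 collects exposure days for 2 mL and for all FVIII, but as totals: they identify an exposed child without linking an event to an infusion. The Appendix A reaction questionnaire, marked as an example, has an infusion field for 2 mL only. Section 10.3.3 records ADVATE dose for procedures without diluent volume. Section 8.6.4 says all exposure is transferred to the CRF from diaries and clinical records, but the diary is voluntary (10.5.2) and its listed content does not name diluent volume.

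**4. Size.** The plan's own figure first: 60 evaluable with 17% dropout gives 60 / (1 − 0.17) = 72.29, rounded up to 73. This reproduces the stated target and does not bear on the point beyond fixing the denominators.

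One affected child moves a subject-level incidence by 1/60 = 1.67 points, or 1/73 = 1.37 points. Exact (Clopper-Pearson) 95% intervals, where for zero events the upper limit is 1 − 0.025^(1/n), are:

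| Events | n = 60 | n = 73 |
|---|---|---|
| 0 | 0% (0 to 5.96) | 0% (0 to 4.93) |
| 1 | 1.67% (0.04 to 8.94) | 1.37% (0.03 to 7.40) |
| 2 | 3.33% (0.41 to 11.53) | 2.74% (0.33 to 9.55) |

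The zero row suits inhibitors better than the primary outcome, which includes fever, headache, nausea and local reactions. Section 6.4.2 reports infusion-site reactions after 2 mL in 2 of 15 children, or 13.3%. Carrying that rate to 60 children purely as an illustration gives 8/60; one more child makes 9/60 = 15.0%, the same 1.67-point step on a larger base.

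**The case against.** The strongest reply is that 10.4 is coherent: a general prohibition followed by a foreseen, pre-accepted deviation, limited to emergent surgery and involving the medical monitor. Section 9.2 also excludes children who need major surgery at enrolment. Much of this stands. The exception is narrow and few children are likely to be affected. What remains is that 8.1, 9.1 and the start of 10.4 are worded without it.

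A second reply is that keeping every event in the safety set is conservative, and that a sensitivity analysis belongs in the SAP, which is not shown. Keeping every event is right, and the absence of a sensitivity table from the protocol would not be a finding by itself. But the protocol fixes sets and outcomes that do not distinguish presentation, and its example form and procedure data do not capture what an SAP would need to distinguish it. Causality is assessed against study product, defined as 2 mL, so the related-events outcome does separate partly; the primary outcome cannot.

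Three stronger readings are tempting and are not supported.

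- **That one misattributed event could change the conclusion.** The study is descriptive, with no hypothesis, threshold or formal sample size (14.1, 14.4). Nothing stated can flip, and the intervals above overlap heavily.
- **That the odds ratio of 4.50 (1.05 to 19.25) for intensive high-dose treatment in section 6.4.1 measures the risk here.** It comes from previously untreated patients and concerns the first 20 exposure days. IAS1 and IAS2 require more than 50, so it cannot apply to them; at most it touches low-exposure children in the all-subjects count.
- **That safety time could be kept or dropped once an event is known.** The medical monitor is to be contacted when the deviation is foreseen, data up to discontinuation stay in the analysis (9.3, 10.6), every inhibitor is an SAE (11.1.1), and an SAE that the investigator learns of after completion must still be reported (11.1.9).

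**Conclusion.** The point holds as one of wording and attribution. Sections 8.1, 9.1 and 10.4 need to be reconciled, and as written any reaction or inhibitor that follows 5 mL or another FVIII is counted as a 2 mL event.

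The effect is probably small: 1.67 points of subject-level incidence per affected child at 60 evaluable subjects, or 1.37 at 73. This assumes that the child's only qualifying event is the one following the other product. The documents do not say how often 5 mL would be used, so the total effect cannot be estimated; the one- and two-event rows are illustrations. The actual CRF is not shown, so the statement about data capture rests on the protocol's listed items and its example form.

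The correction is worth making because it is cheap and because presentation is what this study is meant to assess.

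**What to change.** 1. Reconcile 8.1, 9.1, 9.3 and 10.4 so that one consistent statement covers FVIII other than 2 mL on study and what follows for participation. The clinical rule is for the sponsor.
2. Keep all events in the safety-set primary analysis, as now.
3. Record product and diluent volume for the infusions preceding each reaction, and for the FVIII given as cover in 10.3.3. The latter also helps the surgical and dental set (14.2.5), which takes every procedure whatever presentation covered it, although its outcome is titled as 2 mL effectiveness.
4. List separately the reactions and inhibitors that follow any non-2 mL FVIII.
5. Report the primary incidence and the inhibitor counts with and without children who had any non-2 mL FVIII on study.

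Do not reassign reactions by the last infusion alone. Section 11.1.5 allows reactions beyond 24 hours, so such a rule could remove a delayed 2 mL reaction whenever a 5 mL dose came in between.

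Cost: a wording amendment, one CRF field, and one extra listing or sensitivity table. No additional visits or tests are needed.

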10.5 Data Sources

10.5.1 Source Data

Source data are defined as all information in original records and certified copies of original records of clinical findings, observations, or other activities in a clinical trial that are necessary for the reconstruction and evaluation of the trial. Source data are contained in source documents (original records or certified copies), which may be in paper and/or electronic format. Source data for this study comprise the following: hospital records, medical records, clinical and office charts, laboratory notes, memoranda, subject diaries, recorded data from automated instruments, copies or transcriptions certified after verification as being accurate copies, microfiches, photographic negatives, microfilm or magnetic media, x-rays, subject files, and records kept at the pharmacy, at the laboratories, and at medico-technical departments involved in the clinical study.

The data to be entered directly onto the CRF and to be considered source data are referenced in Section 18.2. The use of subject diaries is described in Section 10.5.2.

10.5.2 Subject Diary

In many centers, it is considered standard practice for subjects with hemophilia to maintain a diary which captures FVIII treatment and disease related data. Therefore, a subject diary will be provided to each subject at the screening visit, as needed, to help with the standardization of data collection method. Nevertheless, the completion of the diary is a voluntary effort by the individual subject or subject's legally authorized representative. A subject diary should allow for capture of the following information:

- Infusion log
- AEs
- Bleed events, date-time and anatomical location
- Subjective hemostatic effectiveness rating for each bleeding episode treated
- Total units of ADVATE reconstituted in 2 mL SWFI administered to treat each bleeding episode

- Number of ADVATE reconstituted in 2 mL SWFI infusions used to treat each bleeding episode
- Number of days subject missed from school/daycare due to each bleeding episode
- Number of days subject's caregiver missed from work/school/normal daily activities due to each bleeding episode

All AEs regardless of causality, bleed occurrences and location, subjective hemostatic effectiveness ratings for each bleeding episode treated, total units of ADVATE reconstituted in 2 mL SWFI administered and infusions used to treat each bleeding episode, and number of days missed by subject from school/daycare, respectively and by caregiver from work/school/normal daily activities, recorded in subject diary during study participation period will be transcribed onto the CRF.

The subject diary will serve as source documentation. Entries in the subject diaries will be transcribed onto the appropriate CRFs. Any entry on the CRF that does not correspond with an entry in the subject diary will be explained by the investigator on the relevant subject diary page.

10.6 Subject Completion/Discontinuation

A subject is considered to have completed the study when he/she ceases active participation in the study because the subject has, or is presumed to have, completed all study procedures according with the protocol (with or without protocol deviations). Reasons for completion/discontinuation will be reported on the Completion/Discontinuation CRF, including: completed, screen failure, adverse event (eg, death), discontinuation by subject (eg, lost to follow-up [defined as 3 documented unsuccessful attempts to contact the subject], dropout), physician decision (eg, protocol violation(s)), study terminated by sponsor, or other (reason to be specified by the investigator, eg, technical problems). Regardless of the reason, all data available for the subject up to the time of completion/discontinuation should be recorded on the appropriate CRF.

Every effort will be made to have discontinued subjects complete the study completion/termination visit. The reason for discontinuation will be recorded on the CRF, and data collected up to the time of discontinuation will be used in the analysis and included in the clinical study report. Assessments to be performed at the termination visit (including in cases of withdrawal or discontinuation) can be found in Supplement 21.1 Schedule of Study Procedures and Assessments.

10.7 Procedures for Monitoring Subject Compliance

There is no procedure for monitoring subject compliance. All treatment regimens and monitoring schedules will be determined by the treating physician. The protocol does not require for any additional testing or monitoring than what is judged necessary by the treating physician.

11. ASSESSMENT OF SAFETY

11.1 Adverse Events

The following data will be collected at **interval and termination visits**:

- All serious and non-serious AEs, regardless of causal relationship to ADVATE reconstituted in 2 mL SWFI, including but not limited to
 - ➤ All local and general, hypersensitivity and infusion related-reactions
 - > FVIII inhibitor titer

An AE is defined as any untoward medical occurrence in a subject administered study product that does not necessarily have a causal relationship with the treatment. An AE can therefore be any unfavorable and unintended sign (including an abnormal laboratory finding), symptom (eg, rash, pain, discomfort, fever, dizziness, etc.), or disease (eg, peritonitis, bacteremia, etc.) temporally associated with the use of the study product (ie, ADVATE reconstituted in 2 mL SWFI), whether or not considered causally related to the study product. An AE includes any event, regardless of the presumed causality between the event and the study product.

